Analysis of stool metabolomics: We will use both the non-targeted Global Metabolomics and the TrueMass™ Complex Lipid Panel (Metabolon, Inc.) to examine the effect of intervention on the stool metabolite profile. The Global Metabolomics platform quickly and accurately identifies and quantitates more than 1,000 metabolites with less than 4.5% median process variability and is compatible with almost any sample type. The TrueMass™ Complex Lipid Panel provides absolute quantitation of 14 lipid classes, including principle phospholipid, sphingolipid and neutral lipid classes. It also provides molecular species concentrations and complete fatty acid composition of each lipid class, thereby offering unparalleled insight into the lipidome. The

resultant data will be imported into Surveyor Web Tools (Metabolon, Inc.) for intuitive data visualization and easier interpretation. We will also use the MetaboLync® Client Portal provided by Metabolon, Inc. to perform comprehensive, in-depth analysis, such as the heat map tool, the pathway enrichment tool, and the Pathway Visualizations Tool. The treatment effect on metabolites (log-transformed whenever needed) will be first assessed by paired t-test and then by linear mixed effects model that includes treatment status (pre/post-treatment), duration of treatment, and other major factors that may influence the metabolomics, including major dietary and lifestyle patterns (e.g., fiber intake, physical activity, body mass index, smoking, and alcohol intake).

Analysis of Urinary PGE-M: We will measure PGE-M (11 α -hydroxy-9, 15-dioxo-2,3,4,5-tetranor-prostane 1,20-dioic acid) levels in baseline/pre-treatment and post-treatment urine samples using liquid chromatography-mass spectrometry (LC/MS) as previously described.¹⁴¹ 0.5mL of each urine specimen will be stabilized by conversion to the *O*-methyloxime derivative and purified by C18 solid phase extraction with subsequent addition of the *O*-methyloxime derivatized deuterium-labeled internal standard (custom synthesis). Liquid chromatography (LC) will be performed on an Acquity BEH C18 column (2.0 \times 50 mm, 1.7 μ m particle, Waters Corporation, Milford, MA, USA) connected to a Waters Acquity I-Class UPLC system and delivered to a Waters Xevo TQ-S Micro triple quadrupole mass spectrometer (Waters Corporation, Milford, MA, USA).

13.7 Reporting and Exclusions

Participants who never start protocol therapy or do not return for final flexible sigmoidoscopy and sample collection will be considered inevaluable and will be excluded from all analyses.

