6. DOSING DELAYS/DOSE MODIFICATIONS

Dose reduction will be made as indicated in the following table(s). The descriptions and grading scales found in the revised NCI Common Terminology Criteria for Adverse Events (CTCAE) version 5.0 will be utilized for dose reduction. A copy of the CTCAE version 5.0 can be downloaded from the CTEP website

http://ctep.cancer.gov/protocolDevelopment/electronic_applications/ctc.htm.

When the study staff is informed of a GI-related adverse event, dose reduction may be considered, according to the following dose de-escalation schema.

Dose Level	AMR 101 Dose
Initial Dose	4 grams/day, for the full course of the intervention
Level -1	2 grams/day, for the rest of the intervention period

Criteria for treatment reduction and suggested guidelines for the management of GI toxicities related to AMR 101 are summarized below. These general guidelines may be modified at the discretion of the investigator based on best clinical judgment at that time, but the reason for these reductions must be documented in the medical record. Any GI toxicities related to AMR 101 should be managed according to standard medical practice. These dose reductions are guidance for clinicians for use of this standard therapy.

Participants who report GI-related adverse events including but not limited to the adverse events described in the tables below will be offered dose reduction as well as the option to withdraw from the study.

Nausea	Management/Next Dose for AMR 101
≤ Grade 1	Reduce to dose level -1
Grade 2	Reduce to dose level -1
Grade 3	Reduce to dose level -1
Grade 4	Reduce to dose level -1

Vomiting	Management/Next Dose for AMR 101
≤ Grade 1	Reduce to dose level -1
Grade 2	Reduce to dose level -1
Grade 3	Reduce to dose level -1

Vomiting	Management/Next Dose for AMR 101
Grade 4	Reduce to dose level -1

Diarrhea	Management/Next Dose for AMR 101
≤ Grade 1	Reduce to dose level -1
Grade 2	Reduce to dose level -1
Grade 3	Reduce to dose level -1
Grade 4	Reduce to dose level -1

Constipation	Management/Next Dose for AMR 101
≤ Grade 1	Reduce to dose level -1
Grade 2	Reduce to dose level -1
Grade 3	Reduce to dose level -1
Grade 4	Reduce to dose level -1

Stomach pain	Management/Next Dose for AMR 101
≤ Grade 1	Reduce to dose level -1
Grade 2	Reduce to dose level -1
Grade 3	Reduce to dose level -1
Grade 4	Reduce to dose level -1

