7.2 Adverse Event Characteristics

- **CTCAE term (AE description) and grade:** The descriptions and grading scales found in the revised NCI Common Terminology Criteria for Adverse Events (CTCAE) version 5.0 will be utilized for AE reporting. All appropriate treatment areas should have access to a copy of the CTCAE version 5.0. A copy of the CTCAE version 5.0 can be downloaded from the CTEP web site https://ctep.cancer.gov/protocoldevelopment/electronic_applications/docs/CTCAE_v5_Quick_Reference_8.5x11.pdf
- **For expedited reporting purposes only:**
 - AEs for the agent(s) that are listed above should be reported only if the adverse event varies in nature, intensity or frequency from the expected toxicity information which is provided.
 - Other AEs for the protocol that do not require expedited reporting are outlined in the next section (Expedited Adverse Event Reporting) under the sub-heading of Protocol-Specific Expedited Adverse Event Reporting Exclusions.
- **Attribution** of the AE:
 - Definite – The AE *is clearly related* to the study treatment.
 - Probable – The AE *is likely related* to the study treatment.
 - Possible – The AE *may be related* to the study treatment.
 - Unlikely – The AE *is doubtfully related* to the study treatment.
 - Unrelated – The AE *is clearly NOT related* to the study treatment.

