7.3 Expedited Adverse Event Reporting

7.3.1 Investigators **must** report to the Overall PI any serious adverse event (SAE) that occurs after the initial dose of study treatment, during treatment, or within 30 days of the last dose of treatment on the local institutional SAE form.

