7.5 Routine Adverse Event Reporting

All Adverse Events **must** be reported in routine study data submissions to the Overall PI on the toxicity case report forms. **AEs reported through expedited processes (e.g., reported to the IRB, FDA, etc.) must also be reported in routine study data submissions.**

[figure not shown]

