13.7.1 Evaluation of Toxicity

N/A

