13.7.2 Evaluation of the Primary Efficacy Endpoint

The primary endpoints will be determined for all patients who complete the final flexible sigmoidoscopy and sample collection, regardless of whether the patient complied with study drug use.¹⁴⁴

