13.7.3 Evaluation of the Secondary Endpoints

The secondary endpoints will be determined for all patients who complete the final flexible sigmoidoscopy and sample collection, regardless of whether the patient complied with study drug use.¹⁴⁴

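### Section 13.7 drops every non-returner from all analyses, including people who took drug, and 13.7.1 is N/A, so section 13 gives no safety denominator

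*Combined protocol and SAP*

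**What the plan says.** Section 13.7 sets a single exclusion rule. It covers participants who never start therapy and also those who "do not return for final flexible sigmoidoscopy and sample collection will be considered inevaluable and will be excluded from all analyses". Nothing in it separates biomarker analyses from safety summaries, or dosed from undosed people.

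The next heading, "13.7.1 Evaluation of Toxicity", is followed only by N/A. Section 13.7.2 evaluates the primary endpoint in "all patients who complete the final flexible sigmoidoscopy and sample collection, regardless of whether the patient complied with study drug use". Section 13.7.3 does the same for the others: "The secondary endpoints will be determined for all patients who complete the final flexible sigmoidoscopy and sample collection", again whatever the compliance.

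Other sections deal with safety data:

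- Section 6: participants who report GI adverse events "will be offered dose reduction as well as the option to withdraw from the study".
- Section 7.2: the CTCAE "version 5.0 will be utilized for AE reporting", and each event is given an attribution category.
- Section 7.3.1: investigators report any serious AE "that occurs after the initial dose of study treatment, during treatment, or within 30 days of the last dose of treatment".
- Section 7.5: all AEs must "be reported in routine study data submissions to the Overall PI on the toxicity case report forms".
- Section 5.7: people taken off therapy are followed by phone for a month, and those removed for unacceptable AEs until the event resolves or stabilises.
- Section 10 schedules weekly AE calls, and section 12.2 has the study team review toxicity data.
- Sections 5.6 and 5.8: the reason for leaving therapy or study goes into the eCRF.

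**The concern.** In a single-arm trial the AE table is a plain count over a denominator, so who is counted is the whole of the method. Section 13 does not name that denominator. The only rule there that could be applied removes people by a criterion that may be linked to toxicity, namely not coming back for a second sigmoidoscopy.

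The protocol itself contains the route. The first dose follows the baseline sigmoidoscopy (section 5.1), so a person can be dosed and then not return. Section 6 offers withdrawal from the study to people with GI events. Section 7.1.1.1 notes that mild to moderate GI events have been reported by participants in this study as well as others. The documents do not say that anyone has withdrawn because of one.

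Section 14 commits to making the results public. An AE summary published under 13.7 as written would leave out dosed people whose events are already on the toxicity forms.

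**Working it through.** **1. The plan's own figures (section 13.2).** Inputs: mean change 3.0%, SD of the paired difference 9.0%, two-sided 0.05, power 80%, drop-out 10%, enrolment 80. The effect size is 3.0/9.0 = 0.333. An exact noncentral-t calculation for the paired t-test gives n = 73 with power 0.802, so the stated 73 is reproduced. This point disputes none of these figures. It uses only the 80 and the 10%.

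**2. Size of the group that 13.7 removes.**
- Not returning: 80 × 0.10 = 8.
- Returning: 80 − 8 = 72.

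**3. Share of dosed people left out.** Let d be the number of the 8 non-returners who took drug. The documents do not give d, so the range is shown. Assume that all 72 returners were dosed. The dosed set is 72 + d, and the share omitted is d/(72 + d).

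| d | Dosed set | Share omitted |
|---|---|---|
| 0 | 72 | 0/72 = 0% |
| 4 | 76 | 4/76 = 5.3% |
| 8 | 80 | 8/80 = 10.0% |

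**4. Largest possible effect on an AE rate.** Let r be the rate in returners and q the rate in dosed non-returners. The rate in all dosed people is (72r + dq)/(72 + d). Subtracting r gives d(q − r)/(72 + d). Since q and r lie between 0 and 1, the absolute difference is at most d/(72 + d): 0, 5.3 or 10.0 percentage points. The limit is reached only if every dosed non-returner has the event and no returner does, or the reverse.

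**5. Direction.** This step uses assumed counts for illustration only. Suppose 4 of 72 returners have an event: 4/72 = 5.6%. With d = 8, if none of the 8 has it, the all-dosed rate is 4/80 = 5.0%. If all 8 have it, the rate is 12/80 = 15.0%. The returner-only figure is 5.6% in both cases, so it can be too high or too low.

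**6. Is a safety set defined elsewhere?** Sections 5.7, 7.2, 7.3.1, 7.5, 10 and 12.2 cover collection, grading, reporting, follow-up and review. None names a population or denominator for a summary. Sections 13.5 and 13.6 describe biomarker analyses only.

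**The case against.** The strongest reply is that nothing planned goes wrong. The objectives in sections 1.2 and 1.3 are biomarkers, section 11 says that only laboratory endpoints are used, and the drug is marketed and given at its standard dose. With 13.7.1 marked N/A there is no planned toxicity analysis to distort, and in context the phrase about all analyses most naturally means the biomarker analyses of 13.5 and 13.6. Safety reporting under 7.5 and 12.2 is also not restricted to people who return.

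Most of this stands. No planned result is biased, and oversight during the trial does not depend on 13.7. It does not close the gap, however. Sections 7.5 and 12.2 concern submission and monitoring and give no denominator, and the wording of 13.7 has no limit to biomarkers. Whoever prepares the AE results for publication has one written rule in section 13, and it points the wrong way.

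A second reply concerns what the exclusion does. A reader might infer that, because 13.7.2 and 13.7.3 already describe completers, the wider words in 13.7 can only be aimed at adverse events. The documents do not support that. Those two sections say who is included and do not say that others are left out. The mixed models in 13.5 and 13.6 could technically take a baseline-only sample. Section 13.7 is the sentence that expressly keeps such samples out, so it does real work for the biomarkers and must be kept for them.

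The size is also open to challenge: 10% is an algebraic ceiling and not an estimate. That is correct, and it is used here only as a ceiling.

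**Conclusion.** The point holds for the analysis and public reporting of adverse events, and no further. Section 13 defines no safety denominator, and its single exclusion rule, followed as written, would remove dosed people who left from any AE summary.

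At 10% drop-out this is at most 8 of 80 dosed people, and at most 10.0 percentage points on any AE rate, in either direction. This rests on the plan's drop-out figure, on all returners having been dosed, and on a value of d that the documents do not give. The AE rates of people who leave are not given either.

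A reader might infer that events in people who withdraw go unrecorded, or that the tissue EPA result is biased by this rule. Neither follows. Events are collected, reported and followed regardless of return, and the pre–post comparison needs the final sample in any case.

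The change should be made because it is cheap and the rule misleads as written. It does not threaten the primary result.

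**What to change.** 1. In section 13.7, limit the exclusion of non-returners to all biomarker analyses, and name the mixed models as included. Limiting it to the paired tests alone would leave it open whether baseline-only samples enter the models. With this wording they stay out and no biomarker analysis changes.
2. In section 13.7.1, replace N/A with one descriptive table of all AEs by CTCAE version 5.0 term, grade and attribution, in everyone who took at least one dose, drawn from the existing toxicity forms. Beside it, give the number of non-returners and the reasons already recorded in the eCRF.

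The cost is a wording change and one extra table, with no new data collection. The downside is that reported AE rates may look less favourable than rates in returners alone. No change to dosing, withdrawal or other clinical rules is proposed.

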13.7.1 Evaluation of Toxicity

N/A

13.7.2 Evaluation of the Primary Efficacy Endpoint

The primary endpoints will be determined for all patients who complete the final flexible sigmoidoscopy and sample collection, regardless of whether the patient complied with study drug use.¹⁴⁴

13.7.3 Evaluation of the Secondary Endpoints

The secondary endpoints will be determined for all patients who complete the final flexible sigmoidoscopy and sample collection, regardless of whether the patient complied with study drug use.¹⁴⁴

APPENDIX A

VIOSCREEN OVERVIEW

Product Background

VioScreen is a scientifically validated, dietary assessment tool that generates an accurate analysis of a subject's dietary behavior in about 20 minutes.

The assessment allows for the evaluation of subjects against a typical North American diet. This graphical online assessment consists of approximately 1,200 food images. Subjects are shown a set of foods within a food group from which they select only foods consumed at least once a month over the past three months. For each food identified, the system prompts the subject to select the frequency and portion size typically consumed. When needed, VioScreen branches to collect more relevant data. For example, if the subject lists "coffee," VioScreen prompts to see if sugar or milk is added and, if so, what kind of milk.

Subject responses are digitally stored in real time, verified for completeness, and analyzed to create an accurate and detailed nutritional profile with over 160 nutrient and food components, top foods with key nutrients, current and recommended eating patterns, Body Mass Index and Estimated Energy Requirement. Responses and analysis are immediately accessible to the researcher via VioScreen's administrative interface. This straight through process eliminates the need for lengthy and costly interviews or error prone paper-based questionnaire processing.

VioScreen's administrative interface is not just for data access, it makes the management of the entire process easy. Researchers are able to define organizations and protocols, assign user roles, import subject data, view results and export results to a standard file format for import to analytical software.

Hosting Environment & Backup

All data is stored in the latest version of Microsoft SQL Server database. The web server and database server reside on their own secure environments separated from other servers through a secure router implementation. All server access requires individual user level access via VPN, each user is required to update their password after 45 days, and all access is logged and reported. The application and database is backed up through highly secure cloud based services. The servers are cloud based and each server's operating system (Windows OS) is updated as new patches are released. HIPAA compliance is supported through the use of tools like Idera's SQL Server Compliance Manager for auditing sensitive data, monitoring alerts, and potential threat detection. Any unauthorized access to any environment or application is reported and tracked within the Windows OS.

System & Data Access

VioScreen is web-based application so there is nothing to install or manage. It has interactive data input and retrieval over the internet via transport layer security so the only requirement is an internet connection and access to www.vioscreen.com. All access to the application is secured through encrypted password access and each session is timed out after 15 minutes of inactivity

for both subjects and researchers.

Upon account setup new customers will receive a study administrator account. This account allows the study administrator to do many things including manage their account, set privileges, define protocols, create local administrators and create subjects. As part of the protocol definition, the study administrator is able to create subjects by a unique SubjectID to ensure participant confidentiality. All data is available in real-time to researchers via the export functionality available via the administrative functionality. Data is exported to a .csv format for easy import to any analysis software.

VioScreen Nutritional Assessment Food List

This document lists foods that are included as part Viocare's nutritional assessment. This is an electronic assessment that is administered online and includes integrated decision tree logic that prompts users to answer additional relevant questions (i.e. by choosing coffee, the system will ask if cream or sugar is used).

Food List

- Sweetened cereal (such as Apple Jacks®, Cocoa Puffs®, Fruit Loops®, Lucky Charms®, Trix®)
- Highly-fortified cereal (such as Total®, Product 19® and Smart Start®)
- Mostly or all whole grain cereal (such as Cheerios®, Grape-Nuts, Quaker Natural Granola®, Raisin Bran and Shredded Wheat)
- Standard cereal (such as Corn Flakes, Kellogg's Crispix® and Rice Krispies®)
- What type of milk or creamer did you put on cold cereals
- Whole grain or partial whole grain cooked cereal such as regular oatmeal (rolled oats), cream of brown rice, Roman Meal®
- Standard cooked cereals, such as cream of wheat, instant or quick-cooking oatmeal, cream of rice, grits, Malt-O-Meal®
- What type of milk or creamer did you usually use to cook the cereal?
- What type of milk or creamer did you usually put on cooked cereals?
- Pancakes, French toast and waffles
- Muffins, scones, croissants and biscuits
- White breads, including bagels, rolls and English muffins
- Whole grain breads, including whole grain bagels, rolls and English muffins
- Cornbread and corn muffins
- Corn tortillas
- Flour tortillas
- Eggs
- Egg Whites
- Tofu or soy breakfast sausage or other breakfast meat
- Bacon and breakfast sausage
- Tofu or soy cold cuts, hot dogs or deli meat substitutes
- Hot dogs and sausage, low or reduced fat
- Hot dogs and sausage, regular, not low fat
- Ham, turkey and low fat lunch meats

- Bologna, salami, Spam® and all other regular lunch meats
- Beef, pork, ham and lamb
- Veggie soy or tofu burgers or ground meat substitute
- Hamburgers, meatloaf and other ground meat
- Liver, chicken liver and organ meats
- Soy or tofu chicken or turkey
- Fried chicken, including nuggets and tenders
- Chicken and turkey, roasted, grilled, broiled or stewed
- Fried fish, fish sandwiches and fried shrimp and oysters
- Shrimp, oysters, crab and lobster
- White fish, broiled or baked, such as cod, halibut and snapper
- Dark fish, broiled or baked, such as salmon, trout and mackerel
- Canned tuna and tuna salad
- Packaged mixed dishes with soy or tofu
- Stew, pot pies, curries and casseroles with meat and chicken
- Chili with meat and beans
- Spaghetti, lasagna or other pasta with tomato and meat sauces (whole grain, regular)
- Spaghetti, lasagna or other pasta with tomato sauce (no meat) (whole grain, regular)
- Spaghetti and other pasta with oil, cheese or cream sauce, including macaroni and cheese
- Pizza (whole grain, regular)
- Asian-style (stir-fried) noodles and rice, such as chow mein, fried rice and Pad Thai
- Japanese noodles, such as Udon and Soba
- Burritos, tacos, tostados and quesadillas
- Enchiladas and tamales
- Tofu (all types), including low fat, flavored, marinated and smoked
- Tempeh (all types)
- Vegetable, minestrone and tomato soup
- Cream soups, such as chowders, potato and cheese
- Bean soups, such as pea, lentil and black bean
- Chicken noodle and other broth soups
- Miso soup
- Ramen noodle soup
- Cottage cheese and ricotta cheese (regular, low fat, nonfat)
- Soy cheese
- Sour cream (regular, low, nonfat)
- Cheese (regular, low, nonfat)
- Soy yogurt
- Greek Yogurt (sweetened, regular, low fat, nonfat)
- Yogurt (plain, sweetened, regular, low fat, nonfat)
- Salad greens (lettuce and spinach)
- Fresh tomatoes
- Carrots (raw)
- Green peppers and green chilies (raw)
- Red peppers and red chilies (raw)
- Avocado and guacamole
- Coleslaw

- Potato, macaroni and pasta salads
- Salad dressing
- Broccoli
- Cauliflower, cabbage and brussels sprouts
- Green beans and string beans
- Carrots (cooked)
- Green peas
- Corn and hominy
- Red peppers and red chilies (cooked)
- Green peppers and green chilies (cooked)
- Onions and leeks
- Summer squash and zucchini
- Winter squash, such as acorn and butternut
- Yams and sweet potatoes
- Kale, mustard greens and collards (cooked)
- Spinach, swiss chard and beet greens (cooked)
- French fries, fried potatoes and hash browns
- Potatoes (boiled, baked or mashed)
- Cooked soybeans or edamame
- Refried beans
- Baked beans, lima beans or all other beans, including chili made without meat
- White Rice
- Brown rice, cracked wheat and other whole grains
- Noodles as a side dish
- Cheese sauce and cream sauce
- Meat gravies
- Ketchup
- Salsa (as dip or on food)
- Mayonnaise and mayonnaise-type spreads
- Salt (in cooking or at the table)
- Soy sauce, tamari, teriyaki sauce, Szechwan sauce and natto
- Fresh garlic
- Apples, applesauce and pears
- Bananas
- Peaches, nectarines and plums
- Apricots - fresh or canned
- Apricots (dried)
- Raisins, prunes and other dried fruit (not apricots)
- Oranges, grapefruit and tangerines (not juice)
- Strawberries, blueberries and other berries
- Cantaloupe, melon and mango (in season)
- Watermelon and red melon
- Grapes, fresh
- Pineapple, fresh and canned
- Cherries, fresh
- Other fruit, including papaya, fruit cocktail or mixed fruit salads

- Soy ice cream
- Other soy desserts such as cheesecake
- Low fat ice cream, frozen yogurt, sherbet or other low or nonfat frozen desserts
- Ice cream and milkshakes
- Pudding, custard and flan
- Doughnuts, pies and pastries
- Cookies or cakes
- Chocolate, candy bars, and toffee
- Life Savers, licorice, jelly beans or other hard candies
- Low or nonfat salty snacks such as pretzels and low or nonfat potato, tortilla and corn chips
- Regular potato, tortilla chips, corn chips and puffs
- Plain popcorn (no butter) or low fat microwave popcorn
- Microwave popcorn (Buttered and regular)
- Soy crackers
- Crackers, such as saltines and SnackWell's (low and nonfat)
- Regular crackers, such as Ritz and Wheat Thins
- Roasted soy nuts and soy nut butter
- Nuts, seeds, peanuts or peanut butter
- Whole grain crackers (low fat and regular)
- Sports bar and meal replacement bar containing soy
- Meal replacement drinks and shakes containing soy or soy protein [SOY]
- Granola bars and cereal bars such as Nutri-Grain Bars
- Sports or meal replacement bars such as Power Bars and Cliff Bars
- Meal replacement drinks and shakes such as Slim-Fast, Ensure and Carnation Instant Breakfast
- Milk as a beverage
- Latte, cappuccino, mocha or hot chocolate
- Coffee (not lattes, cappuccino or mochas)
- Sweet tea and bottled sweetened tea drinks
- Other teas, including black, green and herbal teas
- Sugar
- Diet soft drinks
- Regular soft drinks (not diet)
- Water (tap, bottled and sparkling)
- Tomato juice, V-8 and other vegetable juice
- Orange juice and grapefruit juice
- Other 100% fruit juice such as apple, grape and cranberry
- Fruit drinks fortified with Vitamin C, such as Hi-C, Fruitopia, and Kool-Aid
- Beer (all types)
- Red Wine
- White or rosé wine
- Liquor and mixed drinks

VioScreen Diet Assessment

Cereals and Breads

Section 1 of 20

Food selection... Back Next

Select those foods you eat at least once a month.
 Press the "Next" button if you did not eat any of these foods.

 
Cold breakfast cereals
	 
Cooked breakfast cereals and grits
	 
Pancakes, French toast and waffles

 
Muffins, scones, croissants and biscuits
	 
White breads, including bagels, rolls and English muffins
	 
Whole grain breads, including whole grain bagels, rolls and English muffins

 
Cornbread and corn muffins
	 
Corn tortillas
	 
Flour tortillas

Back Next

Internet | Protected Mode: On 100%

Cereals and Breads

Section 1 of 20

Cold Cereals Back Next

Select those foods you eat at least once a month.
 Press the "Next" button if you did not eat any of these foods.

 
Sweetened (such as Apple Jacks®, Cocoa Puffs®, Fruit Loops®, Lucky Charms®, Trix®)
	 
Highly-fortified (such as Total®, Product 19®, Smart Start®)
	 
Mostly or all whole grain (such as Cheerios®, Grape-Nuts®, Quaker Natural Granola®, Raisin Bran®, Shredded Wheat®)

 
Standard (such as Corn Chex®, Corn Flakes®, Kellogg's Crispix®, Quaker 100% Natural Granola®, Rice Krispies®)
		

Back Next

Done Internet | Protected Mode: On 100%

Cereals and Breads

Section 1 of 20

How often did you eat ...

Back Next

Mostly or all whole grain?
Include Cheerios®, Grape-Nuts®, Quaker Natural Granola®, Raisin Bran® and Shredded Wheat®.

1 per month 2-3 per month 1 per week 2 per week 3-4 per week 5-6 per week 1 per day 2+ per day

Usual portion size?

1/2 cup (small bowl) 1 cup (regular bowl) 1 1/2 cups (large bowl) 2 cups

Skip this question (didn't really eat)

Back Next

Done Internet | Protected Mode: On 100%

Cereals and Breads

Section 1 of 20

Milk on cold cereal

Back Next

Did you use milk on cold cereal?

Yes No

Back Next

Done Internet 100%

Cereals and Breads

Section 1 of 20

Milk on cold cereal

What type of milk or creamer did you usually put on cold cereals?
Select one or two choices.

Cream or half and half	Whole milk	2% milk
1% milk or buttermilk	Nonfat or skim milk	Soy milk
Rice milk	Non-dairy creamer	Don't know

Usual portion size?

 1/2 cup (4 oz)	 1 cup (8 oz)	 1 1/2 cups (12 oz)
-----------------------------------------------------------------------------------------------------	---------------------------------------------------------------------------------------------------	---------------------------------------------------------------------------------------------------------

Done

Internet | Protected Mode: On

Mixed Dishes and Pasta

Section 4 of 20

Food selection...

Select those foods you eat at least once a month.
Press the "Next" button if you did not eat any of these foods.

 Packaged mixed dishes with soy or tofu	 Stew, pot pies, curries and casseroles with meat and chicken	 Chili with meat and beans
 Spaghetti, lasagna or other pasta with tomato and meat sauces	 Spaghetti, lasagna or other pasta with tomato sauce (no meat)	 Spaghetti and other pasta with oil, cheese or cream sauce, including macaroni and cheese
 Pizza		

Done

Internet | Protected Mode: On

Mixed Dishes and Pasta

Section 4 of 20

How often did you eat ... Back Next

Spaghetti, lasagna or other pasta with tomato sauce *made without meat*?

1 per month **2-3** per month **1** per week **2** per week **3-4** per week **5-6** per week **1** per day **2+** per day

Usual portion size?

1/2 cup (small bowl)

1 cup (medium bowl)

1 1/2 cups (large bowl)

2 cups

2 1/2 cups

3 cups

Back Next

Done Internet | Protected Mode: On 100%
